## **Methods and materials**

### **Study design and area**

This study was a hospital-based retrospective cross-sectional study. The study was conducted at the clinic of King Abdul-Aziz Medical City, a tertiary care hospital in Jeddah, Saudi Arabia. Data were collected from the target population through the use of medical records.

### **Study Population**

For this study, we looked at all pregnant patients who visited high-risk pregnancy outpatient clinics at King Abdul-Aziz Medical City in Jeddah from 2021 to 2022. Our focus was on singleton pregnant women who received prenatal care services in Obstetrics clinics at King Abdul-Aziz Medical City. However, to ensure accurate and valid results, we excluded pregnant women with diabetes mellitus or autoimmune diseases. By examining this specific

population of pregnant women, we aimed to investigate potential risk factors and complications associated with high-risk pregnancies.

### **Sampling technique and size**

The sampling technique for this study is non-probability consecutive sampling, which will include all pregnant patients who visited high-risk pregnancy outpatient clinics at King Abdul-Aziz Medical City in Jeddah from 2021 to 2022. The study aims to collect data from all members of the target population instead of sampling from a larger population.

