## **Introduction**

Gestational diabetes mellitus (GDM) is a prevalent condition that affects women across the globe (1). It can lead to a range of complications for both the mother and the baby. The mother may be at a higher risk of developing type 2 diabetes and premature cardiovascular disease, while the baby may experience macrosomia, obesity, hypoglycemia, diabetes, hypertension, and cardiovascular disease in their youth and adulthood (2,3). Early detection of gestational diabetes mellitus (GDM) is crucial to avoid its consequences. In 2010, the International Association of Diabetes and Pregnancy Study Groups (IADPSG) recommended a 2-hour, 75-gram oral glucose tolerance test (OGTT) to diagnose GDM in all pregnant women who did not have a history of overt diabetes during the 24th-28th weeks of pregnancy (4). The oral glucose tolerance test (OGTT) is considered to be the most reliable method, but it can be time-consuming, has poor reproducibility, and is often poorly tolerated during pregnancy (5,6). It is important that pregnant women are not required to attend lengthy clinic sessions for OGTTs, especially during a pandemic. Therefore, simpler yet accurate alternative screening tests should be implemented to reduce the number of OGTTs (7).

Previous research has suggested that fasting plasma glucose (FPG) can be used as a screening technique for gestational diabetes mellitus (GDM) diagnosis. FPG is easier and quicker to use, is less expensive, and can lower healthcare costs associated with universal oral glucose tolerance test (OGTT) screening. However, to accurately diagnose GDM, it is necessary to evaluate the diagnostic performance and determine the ideal FPG cutoff (7). Ping et al. found that gestational diabetes mellitus (GDM) can be predicted through both pre-BMI and initial fasting plasma glucose (FPG) levels before 24 weeks (8). Similarly, Hao et al. found that women who develop GDM tend to have significantly higher FPG levels during the first trimester ( $4.6 \pm 0.3$  mmol/L) compared to women with normal glucose tolerance ( $4.4 \pm 0.3$  mmol/L;  $p=0.001$ ), as well as higher BMI during the same period (9). Additionally, Shin Y et al. reported that a higher BMI is linked to a greater prevalence of GDM. Despite a higher risk

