of developing type 2 diabetes, lifestyle interventions that aim to reduce BMI have the potential to lower the risk of GDM (10). The lack of a standardized agreement on diagnostic criteria and cutoff values for screening tests of FBG and pre-BMI has made it difficult to detect women with GDM early (8). Thus, our study aims to define optimal levels of FBG for the detection of GDM.

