## **Rationale**

The aim of this study is to examine potential risk factors and complications linked to high-risk pregnancies, with a specific focus on gestational diabetes mellitus (GDM). The study intends to offer an understanding of the relationship between GDM and factors such as impaired fasting glucose or impaired glucose tolerance (IFG/IGT), family history of diabetes mellitus (DM), and medical conditions. The study also intends to evaluate the diagnostic performance of screening techniques for gestational diabetes mellitus (GDM), including a history of GDM and impaired fasting glucose (IFG) or impaired glucose tolerance (IGT).

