### **Data Collection Technique and Tool**

The data collection tool was developed and face-validated by two consultants in the field. The tool was designed to collect data from the medical records of the participants, including their fasting blood glucose (FBG) levels and oral glucose tolerance test (OGTT) results. The tool was also used to collect information about the participants' obstetric history, demographic characteristics, and medical conditions.

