### **Data Entry and Statistical Analysis**

The researchers used IBM SPSS Statistics (version 29.0) for data analysis. Categorical variables were presented as proportions, while numerical variables were presented as medians and interquartile ranges due to non-normal distribution. Inferential analyses of categorical variables were conducted using statistical tests such as chi-square and Fisher-Freeman-Halton Exact Tests. Additionally, multivariate analyses were conducted using binary logistic regression, with significance determined by p-values less than 0.05 and inferences made with a 95% confidence level.

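### Does the lack of an OGTT entry requirement, or of a rule for women without an OGTT, bias the FBG cut-off?

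*Combined protocol and SAP*

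**What the plan says.** Study Population describes the cohort by attendance: "we looked at all pregnant patients who visited high-risk pregnancy outpatient clinics at King Abdul-Aziz Medical City in Jeddah from 2021 to 2022". It focuses on singleton pregnancies, and on exclusions it says "we excluded pregnant women with diabetes mellitus or autoimmune diseases". Sampling technique and size repeats the attendance rule, with consecutive sampling "which will include all pregnant patients who visited high-risk pregnancy outpatient clinics". Neither section makes a recorded OGTT a condition of entry.

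Study design and area says the data come from medical records. Data Collection Technique and Tool lists the items abstracted, "including their fasting blood glucose (FBG) levels and oral glucose tolerance test (OGTT) results". It does not say when either was measured, how complete they were, or whether the FBG is a separate measurement or the OGTT's own fasting sample.

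The Introduction closes with the purpose, "our study aims to define optimal levels of FBG for the detection of GDM", and the Rationale adds an aim of assessing the diagnostic performance of screening techniques. Data Entry and Statistical Analysis names descriptive summaries, chi-square and Fisher-Freeman-Halton tests, and says "multivariate analyses were conducted using binary logistic regression". It has no missing-data rule and does not mention women without an OGTT.

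**The concern.** The OGTT is the reference standard. In a retrospective chart study, who has one is decided by routine care and not by a study schedule. The Introduction itself calls the test long and poorly tolerated and mentions the burden of clinic visits in a pandemic, so incomplete testing is plausible. If women with a higher FBG or more risk factors were more likely to be tested, restricting the analysis to tested women gives partial-verification bias: sensitivity looks too high, specificity too low, and the apparent best cut-off drifts upwards. If untested women were instead counted as non-GDM, the outcome of the logistic regression would be misclassified and the FBG odds ratio distorted.

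The FBG level is the study's stated product. A cut-off published with the wrong sensitivity would mislead anyone using it to decide who can skip an OGTT.

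**Working it through.** The plan states no accuracy figure, OGTT coverage or sample size, so there is nothing of its own to reproduce. The check asks how large the bias could be, and what would have to be assumed to get it.

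**Inputs.** The Introduction cites a first-trimester study in which "women who develop GDM tend to have significantly higher FPG levels during the first trimester": 4.6 (SD 0.3) against 4.4 (SD 0.3) mmol/L. The rest is assumed: normal distributions, the Youden index as cut-off rule, a testing probability that steps at 4.5 mmol/L, and 20% GDM prevalence where needed. The completion rates v1 (FBG ≥ 4.5) and v0 (FBG < 4.5) are also assumed.

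**Full testing.** The midpoint is 4.5, and (4.6 − 4.5)/0.3 = 0.333. So sensitivity = specificity = Φ(0.333) = 0.6306, and the Youden cut-off is 4.50.

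**Untested women dropped.**
- Apparent sensitivity = se·v1 / (se·v1 + (1 − se)·v0)
- Apparent specificity = sp·v0 / (sp·v0 + (1 − sp)·v1)

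At 95%/80%:
- Sensitivity = 0.5991 / (0.5991 + 0.2955) = 0.670
- Specificity = 0.5045 / (0.5045 + 0.3509) = 0.590

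At 90%/50%:
- Sensitivity = 0.5675 / (0.5675 + 0.1847) = 0.754
- Specificity = 0.3153 / (0.3153 + 0.3325) = 0.487

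Youden cut-offs come from a grid search on the apparent curves.

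| v1 / v0 (assumed) | Apparent sens / spec at 4.5 | Youden cut-off |
|---|---|---|
| equal | 63% / 63% | 4.50 |
| 95% / 90% | 64% / 62% | 4.51 |
| 95% / 80% | 67% / 59% | 4.52 |
| 90% / 50% | 75% / 49% | 4.57 |
| 95% / 40% | 80% / 42% | 4.60 |
| 100% / 25% | 87% / 30% | 4.64 |
| 50% / 90% | 49% / 75% | 4.43 |

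A cut-off that appears 80% sensitive is truly 77.6% sensitive at 95%/80%, and 70% at 90%/50%.

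**Testing driven by a risk factor, not by FBG.** Assume a factor that raises FBG by 0.2 mmol/L, present in 70% of GDM and 40% of non-GDM women, with everyone who has it tested. If 50% or 25% of women without it are tested, sensitivity goes from 62.6% to 65.8% or 67.8%, specificity from 62.5% to 58.2% or 54.2%, and the cut-off from 4.50 to 4.52 or 4.54.

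**Odds ratio for FBG ≥ 4.5 (crude).**
- P(GDM | high) = 0.2 × 0.6306 / (0.2 × 0.6306 + 0.8 × 0.3694) = 0.299
- P(GDM | low) = 0.2 × 0.3694 / (0.2 × 0.3694 + 0.8 × 0.6306) = 0.128
- Odds ratio = 2.91

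When testing depends only on FBG, dropping untested women leaves this at 2.91, because the risk within each FBG group is unchanged. Counting untested women as non-GDM multiplies the two risks by v1 and v0. The odds ratio becomes 3.49 at 95%/80%, 5.40 at 90%/50% and 1.35 at 50%/90%.

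**What the documents support.** They supply none of the completion rates. The FBG-driven scenarios also need an FBG known before the OGTT was ordered. If the abstracted FBG is the OGTT's fasting sample, it cannot have prompted the test, and only the risk-factor route remains.

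**The case for a change.** The strongest case for a change is that the omission is certain, the remedy is cheap, and the unstated rule can decide the result. At 90%/50% the odds ratio is 2.9 if untested women are dropped and 5.4 if they are counted as non-GDM. The Introduction's reference to OGTT for all women without overt diabetes is background; the methods never say this clinic followed it. A count of untested women, a comparison of tested with untested, and a verification-bias correction such as Begg-Greenes would settle the matter with data already being abstracted.

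The textual part stands: there is no entry requirement and no handling rule, and full coverage cannot be inferred. The rest is weaker. The damaging handling rule appears nowhere in the plan. A woman with no outcome drops out of a logistic regression by default, and she cannot contribute to a sensitivity or specificity. The remedy would write down that default and keep it as the main estimate. Its only new analysis, the correction, cannot be run if the FBG is the OGTT's fasting sample, and otherwise assumes that testing depends only on recorded factors, which the data cannot test. Most of the methods are also written in the past tense, as work already done. The count of women with an FBG, an OGTT and both belongs in any competent report of such a study.

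**Conclusion.** No change to the plan follows. The documents leave a detail unstated, and analysts would ordinarily fill it by analysing women who have both results. They do not show that following the plan gives a wrong answer.

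The possible bias runs from none, when testing is complete or unrelated to FBG and GDM status, through about 4 points of accuracy and 0.02 mmol/L at 95%/80%, to more than 10 points at 90%/50%. In the listed scenarios the cut-off moves by at most 0.14 mmol/L, at 100%/25%; this is not a general bound. The risk-factor illustration gives about 3 to 5 points of sensitivity and 4 to 8 of specificity.

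All of these rest on assumed completion rates, normality (the analysis section reports non-normal numerical variables) and first-trimester values from another population. They show direction and rough scale only. The conclusion would change if chart data showed a material number of untested women, an FBG recorded separately from the OGTT, and testing that clearly followed it.

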### **Data Collection Technique and Tool**

The data collection tool was developed and face-validated by two consultants in the field. The tool was designed to collect data from the medical records of the participants, including their fasting blood glucose (FBG) levels and oral glucose tolerance test (OGTT) results. The tool was also used to collect information about the participants' obstetric history, demographic characteristics, and medical conditions.

### **Data Entry and Statistical Analysis**

The researchers used IBM SPSS Statistics (version 29.0) for data analysis. Categorical variables were presented as proportions, while numerical variables were presented as medians and interquartile ranges due to non-normal distribution. Inferential analyses of categorical variables were conducted using statistical tests such as chi-square and Fisher-Freeman-Halton Exact Tests. Additionally, multivariate analyses were conducted using binary logistic regression, with significance determined by p-values less than 0.05 and inferences made with a 95% confidence level.

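### The plan aims to define optimal FBG levels for detecting GDM but specifies no analysis that selects a level or reports its accuracy

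*Combined protocol and SAP*

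**What the plan says.** The Combined protocol and SAP states two kinds of aim.

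- **Diagnostic.** The Introduction ends: "our study aims to define optimal levels of FBG for the detection of GDM". Earlier it says of fasting glucose that "it is necessary to evaluate the diagnostic performance and determine the ideal FPG cutoff". The Rationale adds an evaluation of how well GDM screening approaches perform, and names history of GDM and IFG/IGT among them.
- **Risk factors.** The Rationale opens: "The aim of this study is to examine potential risk factors and complications linked to high-risk pregnancies". Study Population closes on the same theme.

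Under Data Collection Technique and Tool, the variables taken from the records are described as "including their fasting blood glucose (FBG) levels and oral glucose tolerance test (OGTT) results", together with obstetric history, demographics and medical conditions.

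Data Entry and Statistical Analysis is the whole analysis plan. Categorical variables are summarised as proportions, and numerical variables as medians and interquartile ranges because they are not normally distributed. On testing it says: "Inferential analyses of categorical variables were conducted using statistical tests such as chi-square and Fisher-Freeman-Halton Exact Tests". It then adds binary logistic regression at p<0.05 with 95% confidence. It does not name the regression's outcome or covariates, the coding of FBG, or the variables to be cross-tabulated.

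**The concern.** Defining an optimal level of a continuous marker takes two things: a rule that picks the level, and the accuracy at that level. The analysis section states neither. Its methods suit the risk-factor aim, but they stop at association for the diagnostic one.

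A significant odds ratio does not tell a clinic how many women with GDM a given FBG level would find, or how many without GDM it would flag. The Introduction motivates the study by the wish to reduce the number of OGTTs, so these are the figures a reader would need. With no rule stated, a level in the report would have been chosen in an unplanned way. If it were picked because it looked best in the data, its apparent accuracy would also be optimistic.

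**Working it through.** The plan states no sample size, AUC, sensitivity, specificity or cut-off, so there is no figure of its own to reproduce. The check sets each listed method against the FBG aim and then illustrates the size of the gap.

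**1. What each listed method yields for FBG**

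- *Medians and IQRs.* Even if split by GDM status, they show overlap and carry no rule for choosing a level.
- *Chi-square and Fisher-Freeman-Halton tests.* These apply to categorical variables, and FBG is numerical. If FBG were banded, the table would hold accuracy at the band limits, but no bands are stated.
- *Binary logistic regression.* If FBG enters, the result is an odds ratio with a CI. Building a ROC curve on the model would be a further step that the plan does not state.

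**2. Illustration (not study data and not proposed levels)**

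Inputs from the Introduction: a cited study found that "women who develop GDM tend to have significantly higher FPG levels during the first trimester", at 4.6 ± 0.3 mmol/L against 4.4 ± 0.3 mmol/L in women with normal glucose tolerance. Assumptions: ± is an SD, both groups are normal, and GDM prevalence is 20% (range 10 to 30%). Rounding range: means ± 0.05 and SDs 0.25 to 0.35.

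- Logistic slope = (4.6 − 4.4)/0.3² = 2.22 per mmol/L, so the odds ratio is e^2.22 = 9.2 per mmol/L. This one odds ratio holds whichever cut-off is used.
- AUC = Φ(0.2/(0.3√2)) = 0.68. Rounding extremes: Φ(0.1/(0.35√2)) = 0.58 and Φ(0.3/(0.25√2)) = 0.80.
- Sensitivity = 1 − Φ((c − 4.6)/0.3); specificity = Φ((c − 4.4)/0.3).

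| Level c (mmol/L) | Sensitivity (rounding range) | Specificity (rounding range) |
|---|---|---|
| 4.2 | 0.909 (0.841–0.964) | 0.252 (0.159–0.334) |
| 4.5 | 0.631 (0.557–0.726) | 0.631 (0.557–0.726) |
| 4.7 | 0.369 (0.274–0.443) | 0.841 (0.762–0.919) |

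Per 1000 women at 20% GDM, missed = 200 × (1 − sensitivity) and flagged without GDM = 800 × (1 − specificity).

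- At 4.2: 200 × 0.091 = 18 missed; 800 × 0.748 = 598 flagged.
- At 4.7: 200 × 0.631 = 126 missed; 800 × 0.159 = 127 flagged.

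Varying rounding and prevalence together:

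- Missed at 4.2: from 100 × 0.036 = 4 to 300 × 0.159 = 48.
- Missed at 4.7: from 100 × 0.557 = 56 to 300 × 0.726 = 218.
- Flagged at 4.2: from 700 × 0.666 = 466 to 900 × 0.841 = 757.
- Flagged at 4.7: from 700 × 0.081 = 57 to 900 × 0.238 = 214.

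*Skewed FBG* (shifted gamma, same means and SD, skewness 0.5 to 1.5): AUC 0.69 to 0.72; sensitivity 0.92 to 1.00 at 4.2 and 0.34 down to 0.29 at 4.7. The trade-off remains.

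*Classifying at predicted probability 0.5* does not fill the gap. The implied level is 4.5 + ln((1 − p)/p)/2.22, which is 5.49, 5.12 and 4.88 mmol/L at 10, 20 and 30% GDM, with sensitivity 0.002, 0.04 and 0.17. It follows prevalence, not a diagnostic criterion.

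**3. History of GDM and IFG/IGT**

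For a yes/no item, a 2×2 table against GDM holds the four counts that give sensitivity and specificity, so no cut-off method is needed. The plan names neither these tables nor those measures. The methods sections also give no diagnostic criteria for GDM (the 75 g OGTT recommendation appears only as background in the Introduction) and do not define or time IFG/IGT.

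**The case against.** **The listed methods could be stretched to cover the aim.** A reader might infer that nothing in the analysis section can select an FBG level or show its accuracy. The documents do not support that. The coding of FBG is left open, a test for tables with several categories is named, and a table of FBG bands against GDM would hold accuracy at each band limit. What stands is that no bands, selection rule or accuracy measure is specified. The phrase introducing the tests as examples does not help, because it covers tests of categorical variables only.

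**For history of GDM and IFG/IGT only reporting is missing.** This too goes beyond the text. The cross-tabulations themselves are not named. If IFG/IGT came from the same OGTT that defines GDM, its sensitivity and specificity would be circular.

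**The real aim is risk factors.** The Rationale and Study Population do support a risk-factor aim, and the planned tests suit it. The FBG aim in the Introduction is nevertheless stated without qualification.

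**The illustration is weak evidence.** This is fair. It uses first-trimester values from another study and a normal model, although the plan reports non-normal data. It may not apply at all if FBG is the fasting sample of the OGTT, because index and reference tests would then overlap. It shows only how much the choice of level can matter; the gap itself is established by reading the aims beside the analysis section.

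**Conclusion.** The concern holds as a mismatch between a stated aim and the specified analysis. It is more than missing detail: carried out as written, the plan selects no FBG level and reports no accuracy for one. This needs to be resolved before any FBG level is reported. The conclusion rests on the text alone and assumes only that the Introduction's FBG and FPG refer to the same measurement.

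The size is illustrative. Under the assumptions above, moving between two levels 0.5 mmol/L apart changes missed cases about sevenfold (126/18 = 7.0). The ranges for missed cases at the two levels do not overlap. For history of GDM and IFG/IGT the gap is smaller: the tables and measures need to be named, and the source of IFG/IGT clarified.

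**What to change.** Keep the planned tests for the risk-factor aim. For the FBG aim, do one of the following.

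**(A) Add the analysis** to Data Entry and Statistical Analysis:

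- a ROC analysis of FBG as a continuous variable against OGTT-defined GDM, with the diagnostic criteria stated;
- AUC, sensitivity, specificity, PPV and NPV, each with a 95% CI;
- a cut-off chosen by a stated rule, for example the Youden index or a fixed minimum sensitivity;
- a post hoc label if the data have already been examined, which the section's past tense suggests but does not establish;
- a statement of whether FBG is the fasting sample of the same OGTT, with the conclusion limited if it is.

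The sampled group is "all pregnant patients who visited high-risk pregnancy outpatient clinics", so PPV and NPV should be read for that setting only.

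**(B) Withdraw the FBG cut-off aim** in the Introduction, make clear that the diagnostic-performance aim in the Rationale does not cover FBG, and draw no conclusion about an FBG level.

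**In either case,** report sensitivity and specificity with 95% CIs for history of GDM, and for IFG/IGT only if it was determined separately from the reference OGTT.

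**Optional.** Report how many women lack either test. Apply bootstrap optimism correction: in simulation the apparent Youden index (sensitivity + specificity − 1) was too high by 0.01 to 0.10, assuming n = 200 to 1000 and GDM 10 to 30%, across the rounding range.

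**Cost.** Option A needs SAP wording, a little extra analysis of data already collected, and possibly a return to the records for FBG timing; women without both tests leave this analysis. Option B changes wording in the Introduction and Rationale, and the study loses its cut-off claim.
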